**Laboratory Parameters/Analysis:**

Standard bloodwork, including aPTT, INR and TT (when ordered) within 20 days will be collected. No additional bloodwork will be collected for the study.

**Sample Size Determination:**

There are currently insufficient data upon which to base a sample size. The expected rate of hemorrhagic transformation has never been accurately or prospectively documented in this population. The sample size of 500 patients is expected to be sufficient to demonstrate the frequency of hemorrhagic transformation within this population.

**Statistical Analyses:**

The primary outcome will be occurrence of PH2 at 30 days. Secondary outcomes will be ischemic stroke, any intracerebral hemorrhage, MI and death. In addition we will compare the rate of hemorrhagic transformation in patients started on dabigatran within 7 days of stroke/TIA versus those started  $>7$  days after symptom onset.

Descriptive statistics will be used to describe all outcomes (see protocol section 7.1).

**Canadian Pradaxa Acute Stroke/TIA Safety Study (CPASS)**

**Canadian Stroke Consortium**

**Protocol Version 2.3**

**November 14, 2013**

## **1. Introduction**

### ***1.1 Medical Background***

A transient ischemic attack (TIA) has traditionally been defined as a focal neurologic deficit lasting less than 24 hours, but alternative definitions based on tissue injury have been more recently proposed. This clinical definition has been based on the assumption that TIAs are associated with complete resolution of brain ischemia occurring rapidly enough to cause only transient symptoms and no permanent brain injury, i.e. stroke. A recently completed MRI research study at the University of Alberta indicates that TIA and minor stroke actually represent a continuum of symptoms secondary to brain ischemia. There is also substantial evidence that the period shortly after a TIA or minor stroke is one of elevated recurrent stroke risk; as high as 17% at 3 months. We have previously reported that MRI markers of new infarction are actually present within 7 days of the index event in 18% of patients. TIA and minor stroke can therefore be seen as a sentinel warning for impending major stroke, which offers a potential window for therapeutic intervention. Given the large number of patients who suffer a TIA/minor stroke, it is important to identify and target those patients at highest risk for early recurrence.

*Treatment of Minor Stroke/TIA:* In addition to urgent and rapid investigation of stroke mechanism after TIA/minor stroke, a logical approach to prevent early recurrence is aggressive hyperacute antithrombotic therapy. This treatment strategy is aimed at preventing both recurrent thromboembolism and propagation of existing thrombi. In acute coronary syndrome patients, antithrombotic therapy consists of both anticoagulants (low molecular weight heparin) and combination antiplatelet agents (ASA+high dose clopidogrel, or more recently prasugrel/ticagrelor). In TIA/stroke, the choice of antithrombotic agent varies with the mechanism of cerebral ischemia. The initial therapy in most patients consists of antiplatelet therapy, generally ASA. Combination antiplatelet therapy is sometimes used empirically following TIA/minor stroke, although this may not be an ideal approach either. A previous trial in 392 patients demonstrated a trend towards reduction of recurrent events by day 90 when patients were treated with a combination of ASA and clopidogrel for 90 days (Absolute Risk Reduction = 3.3% [95% CI -1.9, 9.4]), but this was also complicated by excess hemorrhagic events. In unselected ischemic stroke patients (treated irrespective of the presence or absence of atrial fibrillation), the benefits of traditional anticoagulants, particularly heparin, have been consistently offset by an increased incidence of intracranial hemorrhagic complications. The risk benefit ratio appears to be similar in patients with and without atrial fibrillation, although there are significant knowledge and evidence gaps with respect to the timing of anticoagulation in patients with cardioembolic stroke.

#### *Timing of Anticoagulation after Cardioembolic TIA/Stroke:*

It is clearly established that patients with atrial fibrillation who have suffered a stroke/TIA are at high risk for recurrence and require long-term anticoagulation. What is unknown is the optimal timing of anticoagulation after an ischemic stroke has occurred. Following cardioembolic stroke, atrial fibrillation patients are at risk for early recurrent thrombo-embolism. Estimates of the rate of recurrent stroke in this setting vary widely. Previous studies have indicated new ischemic strokes occur at rates anywhere from 3% to 20% within two weeks of the index event. This is the primary rationale for early anticoagulation after cardioembolic stroke. There is some evidence that early anticoagulation is associated with improved outcomes after ischemic stroke. Indeed, it has been shown that early heparin use does reduce recurrent ischemic stroke risk by 2.1%, but this is offset by a 1.7% increase in the rate of HT. Studies of low molecular weight and unfractionated heparin use in acute stroke have generally indicated these agents are associated with moderately increased risk of HT. There are currently no data indicating the frequency of HT associated with early warfarin treatment, without heparin bridging.

Based on the above evidence, current best practice guidelines recommend against urgent anticoagulation in patients with moderate to severe ischemic stroke, however, due to the elevated risk of hemorrhagic transformation (HT) immediately after stroke. A specific time point at which to begin anticoagulation is not recommended in guideline statements. This clinical equipoise has resulted in significant variation in practice patterns. Currently, most CSC physicians base the timing of anticoagulation on clinical severity and infarct size, as seen on CT scan. Most physicians will defer anticoagulation anywhere from 5 to 14 days after ischemic stroke when infarct volume is extensive. In patients with small infarct volumes, assessed with CT or MRI, however, anticoagulation is often begun within 24-72 hours of stroke onset, and in some cases immediately after clinical assessment and CT scan.

The oral direct thrombin inhibitor dabigatran has recently been approved for the primary and secondary prevention of ischemic stroke in patients with atrial fibrillation. Uptake of dabigatran within the Canadian stroke community has been rapid. It has several advantages, relative to warfarin. These include superior protection from cardioembolic stroke, lower rates of intracranial hemorrhage, fixed doses and an absence of coagulation monitoring requirements. Recent discussions amongst Canadian Stroke Consortium (CSC) members have led to the identification of three major outstanding issues related to dabigatran use in patients with cerebrovascular disease:

1. Timing of dabigatran initiation after ischemic stroke/transient ischemic attack (TIA)
2. Safety of thrombolytic agents after ischemic stroke in patients taking dabigatran
3. Optimal management of intracranial hemorrhage in patients taking dabigatran

From both the population health and stroke physician perspectives, the most important clinical problem is the first of these issues. Approximately 20% of acute stroke/TIA is secondary to atrial fibrillation, which is diagnosed at the time of the stroke in the majority of cases. In addition, many patients with known atrial fibrillation are not treated until after an ischemic stroke. The timing of dabigatran initiation after ischemic stroke/TIA is therefore an everyday problem that must be addressed on stroke units across the country.

#### *Dabigatran and Ischemic Stroke:*

Due to the uncertain safety of anticoagulation immediately after stroke, patients with recent stroke (< 2 weeks from symptom onset) have been excluded from clinical trials of newer anticoagulants. Dabigatran is unique in that unlike other antithrombotic drugs studied in cerebrovascular disease, it appears to be associated with a much lower risk of intracranial hemorrhagic complications, and a reduction in ischemic stroke. It is probable that dabigatran can be used safely in patients with acute and subacute ischemic stroke. *We therefore expect that dabigatran will be associated with low rates of HT when administered acutely following cardioembolic stroke.* Patients will therefore be protected from early recurrent stroke, without the concomitant increased risk of hemorrhagic complications associated with other anticoagulants.

#### *Treatment Opportunities:*

The primary benefit of early anticoagulation is a reduction in early recurrent embolic events and therefore improved outcomes. Dabigatran offers the possibility of rapid therapeutic anticoagulation in this setting, a significant benefit over the days to weeks required to achieve a therapeutic INR with warfarin. The complexities associated with initiating warfarin therapy result in a significant treatment gap. Data from the Registry of the Canadian Stroke Network indicate that nearly 50% of patients with cardioembolic stroke are not anticoagulated one year after their index event. Early treatment initiation is expected to result in improved rates of anticoagulation following stroke and greater adherence to therapy. The acute stroke period, when patients are cared for in stroke units, by specialized physicians

represents an opportunity to optimize therapy, including lifelong anticoagulation. If it can be demonstrated that dabigatran can be safely administered early after stroke, as warfarin is used currently, it may ultimately result in higher rates of long-term anticoagulation and consequently a reduction in stroke rates. The current wording in the product monograph stipulating a delay in initiation of dabigatran will result in continued use of warfarin in patients for whom Dabigatran would have greater safety and efficacy.

Given the equipoise and variable practice patterns amongst CSC physicians, the safety of dabigatran after stroke can be effectively addressed using a prospective single arm study design. We have sufficient variability and ischemic stroke patient volume nation-wide to ensure a broad based sample with respect to stroke severity and timing of dabigatran initiation. We have therefore designed a registry of dabigatran treatment following ischemic stroke/TIA. A unique feature of the CPASS registry is the central collection and reading of all imaging data. This will provide invaluable information related to both the nature and predictors of any HT associated with early dabigatran use. The CSC has successfully conducted a phase IV registry of this nature, including central image reading and analysis, in the past (Canadian Alteplase for Acute Stroke Effectiveness Study).

### ***1.2 Drug Profile***

Proprietary name: Dabigatran etexilate (INN). The pro-drug dabigatran etexilate is used in its salt form dabigatran etexilate mesilate (BIBR 1048 MS).

Chirality: Dabigatran etexilate mesilate has no chiral centres and therefore does not form enantiomers. Geometric isomers (tautomers) are possible.

Physical Appearance: Yellow-white to yellow powder. The crystals have a rod-like habit.

Melting Point:  $180 \pm 3$  °C (DSC: 10 K min heating rate)

Dissociation Constants:  $pK_{a1} = 4.0 \pm 0.1$ ,  $pK_{a2} = 6.7 \pm 0.1$

Apparent Partition Coefficient: The partition coefficient of the neutral form (free base) is  $\log P = 3.8$

Hygroscopicity: Non-hygroscopic

pH-Solubility Profile: Solubility is strongly pH dependent with increased solubility at acidic pH. The solubility in water is 1.8 mg/mL

## **2. Canadian Pradox Acute Stroke/TIA Safety Study (CPASS) Rationale and Objectives**

### ***2.1 Rationale***

Ideally, anticoagulation should be started as soon as possible following a stroke/TIA in patients with new or previously diagnosed atrial fibrillation. This prevents early recurrent events and also ensures long-term secondary prevention strategies are implemented at the point of maximum medical contact, which is always at the time of the acute event. The rate of hemorrhagic complications associated with older anticoagulants has never been well characterized, but is recognized as a genuine risk that must be considered and generally delays anticoagulation. As described above, intracranial hemorrhagic complication rates in dabigatran-treated patients are markedly lower than those associated with older anticoagulants. Thus, dabigatran is hypothesized to be an ideal drug for early anticoagulation after acute stroke/TIA.

Although aggressive antithrombotic therapy has been shown to reduce the number of new ischemic events following stroke/TIA, this has always been offset by an increase in the risk of hemorrhagic complications. Dabigatran appears to be much safer with respect to intracranial bleeding and therefore offers a unique treatment opportunity in these high-risk patients. A registry will provide critical reassurance to stroke clinicians concerned about precipitating hemorrhagic transformation. If it can be

demonstrated to be safe, early treatment with dabigatran can be recommended, which may lead to lower rates of cardioembolic stroke recurrence. In addition, this will facilitate optimal treatment of patients who require long-term anticoagulation after ischemic stroke.

## **2.2 Study Objectives**

- 1. Demonstrate the safety of early dabigatran initiation after minor stroke/TIA in patients with atrial fibrillation.*
- 2. Determine the frequency of asymptomatic hemorrhagic transformation after 7 days of dabigatran treatment following stroke/TIA*
- 3. Determine the effect of asymptomatic hemorrhagic transformation on functional and neurological outcome at 30 days.*

## **2.3 Risk-Benefit Assessment**

The risk of recurrent stroke after TIA/minor stroke in AF patients is estimated to range from 3-20%. It is expected that early anticoagulation will reduce the rate of re-embolization by at least 85%. The risk of symptomatic hemorrhagic transformation in patients administered heparin within one week is 1.7%. Intracranial hemorrhagic complication rates in RE-LY were 1/3 that of warfarin. We hypothesize that a similar pattern of increased safety with respect to intracranial hemorrhagic complications will be seen in the acute setting. Thus, symptomatic hemorrhagic transformation rates of 0.6% are expected, which is comparable to the rate seen in patients treated with antiplatelet agents alone. The major expected benefit of this study is early anticoagulation, resulting in fewer cases of prolonged delays to the initiation of appropriate secondary prevention therapy.

## **3. Canadian Pradox Acute Stroke/TIA Safety Study (CPASS) Design**

**3.1 Study Aim and Design:** The primary aim of the CPASS registry is to demonstrate the safety of early anticoagulation with dabigatran following cardioembolic stroke. CPASS is a prospective open label single arm observational study. Safety will be established by demonstrating low rates of hemorrhage in this setting.

**3.1.1 Administrative Structure:** CPASS is a Canadian Stroke Consortium led study. The study coordinating centre is at the University of Alberta. Case report forms and data monitoring will be completed electronically, using an online EDC system. All imaging data will be read centrally at the Stroke Imaging Laboratory at the University of Alberta.

**3.2 Study Design Considerations:** A randomized controlled design was considered (dabigatran versus warfarin). This is considered impractical for a number of reasons. Novel oral anticoagulants are recommended as first line agents for stroke prevention in AF patients by the Canadian Cardiovascular Society. These agents are associated with improved safety with respect to bleeding complications. This makes randomization of a patient to warfarin who would otherwise be prescribed dabigatran somewhat ethically dubious. In addition, a randomized design would necessitate a very large study, which would not be completed in a reasonable period of time. A registry design allows us to address the question of safety in a systematic fashion. A safety threshold has been defined for any anticoagulant use early after stroke, based on the rates of warfarin-associated intracranial hemorrhage, which have been reported to be 0.5 to 2.5 per 100 patient years. The registry design therefore permits determination of whether or not dabigatran is within this threshold. Finally, the systematic collection of clinical and imaging data will allow us to determine any risk factors for hemorrhagic transformation associated with early anticoagulation.

**3.3 Selection of Population.** A log of all patients included in the study (consent obtained) will be maintained at the trial coordinating centre, irrespective of whether they are treated or not. Only patients actually treated with dabigatran will be followed in the registry. Basic patient demographics, ethnicity, stroke severity (NIHSS), medications, including previous warfarin use, previous stroke/TIA, other co-

morbidities, particularly hypertension, diabetes, hypercholesterolemia and ischemic heart disease, CHADS-Vasc, HAS-BLED, history of gastrointestinal or other hemorrhage will all be recorded (**Appendix 1**).

**3.3.1 Patients.** Male and female patients with acute TIA or ischemic stroke will be recruited from the Emergency Departments and stroke units at CSC investigator sites. All patients will have documented evidence of atrial fibrillation (permanent or paroxysmal). Informed consent will be obtained from patients or surrogate decision makers prior to enrolment in all cases.

**3.3.2 Inclusion Criteria.** All patients will be 18 years or older. Eligible patients will have ischemic stroke (NIHSS score  $\leq 3$ ) or TIA (complete resolution of focal neurological deficits within 24 hours) and atrial fibrillation (paroxysmal or persistent). The decision to treat with dabigatran and the timing of the first dose will be determined by the attending physician, independent of the registry. In cases where stroke onset time cannot be established, it will be considered to be the time when the patient was last known to be well. All patients will have a CT scan or MRI, with findings consistent with an ischemic etiology of symptoms. Patients taking warfarin *prior to* the stroke/TIA will be eligible, but INR must be  $\leq 1.5$  prior to initiation of dabigatran.

**3.3.3 Exclusion Criteria.** Patients in whom dabigatran is contraindicated according to the Canadian product monograph will not be eligible, i.e. severe renal failure or significant ongoing bleeding risk, will not be eligible. These specific contraindications in the Canadian product monograph at the time are:

- Severe renal impairment (CrCl  $< 30$  mL/min)
- Hemorrhagic manifestations, bleeding diathesis, or patients with spontaneous or pharmacological impairment of hemostasis
- Lesions at risk of clinically significant bleeding, e.g. extensive cerebral infarction (hemorrhagic or ischemic) within the last 6 months, active peptic ulcer disease with recent bleeding
- Concomitant treatment with strong P-glycoprotein (P-gp) inhibitors, i.e. oral ketoconazole
- Known hypersensitivity to dabigatran or dabigatran etexilate or to any ingredient in the formulation or component of the container
- Concomitant treatment of dabigatran etexilate with any other anticoagulant, including unfractionated heparin (UFH), except at doses used to maintain a patent central venous or arterial catheter, low molecular heparins (LMWH), such as enoxaparin and dalteparin, heparin derivatives, such as fondaparinux, anti-thrombin agents, such as bivalirudin, and oral anticoagulants, such as warfarin, rivaroxaban, apixaban, except under circumstances of switching therapy to or from dabigatran
- Presence of prosthetic heart valve(s) requiring anticoagulation due to valvular status itself

Patients with a history of symptomatic ischemic stroke prior to the index event will not be eligible. All patients taking dabigatran or any other novel oral anticoagulant (including all Factor Xa antagonists) prior to the stroke will be ineligible. Individuals on warfarin at the time of the incident event are eligible, provided the INR is  $\leq 1.5$  prior to initiation of dabigatran.

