## **5. Variables and Assessment.**

**5.1.1 Effectiveness.** This is a registry of the safety of early anticoagulation (see 5.2). A measure of the effect of early anticoagulation will be assessed; the rate of new ischemic stroke/TIA occurrence within the 30-day study period will be recorded. It is recognized that the event rate will be low and the study is neither designed, nor powered to demonstrate a decrease in early ischemic stroke rates.

**5.1.2 Primary Outcome (Safety).** The primary study outcome measure is the symptomatic hemorrhagic transformation rate (PH2 associated with clinical deterioration, defined as worsening of NIHSS score of 4 or more points, within 30 days of initiating dabigatran therapy).

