### **6.2 Details of Study Procedures**

**6.2.1 Screening and run-in procedures.** NA.

**6.2.2 Treatment Period.** Patients will be treated long-term with dabigatran if deemed appropriate by the attending physician and the patient is in agreement. The study outcome event period is 30 days from drug initiation. The SAE reporting period is an additional 7 days.

The time from symptom onset to dabigatran initiation will be recorded in the CRF. In all cases, dabigatran will be prescribed by a stroke neurologist participating in the registry. The location of the patient at the time of dabigatran initiation will be recorded (inpatient/outpatient/Emergency Department).

**6.2.3. End of Trial and follow-up.** The registry data collection period will be complete after 30 days.

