## **7. Statistical Methods and Sample Size**

**7.1 Statistical Analysis and Sample Size Considerations:** The registry will include 500 patients. This sample size is considered adequate to ensure inclusion of a significant number of patients treated at a range of time points within the post-stroke period. The primary analysis will be done on an Intention

To Treat basis. We will also complete a sensitivity analysis on individuals who discontinued dabigatran treatment and/or switched to other antithrombotic agents. Based on the inclusion/exclusion criteria, there will not be any individuals taking dabigatran concomitantly with other antithrombotic drugs.

The primary and secondary outcomes will be defined with descriptive statistics. The rate of PH2 (and all other forms of hemorrhagic transformation) will be defined as a ratio (%) of the total number of patients enrolled in the study (ITT analysis).

The primary stratification variable is warfarin use prior to the TIA/minor stroke. The secondary strata are 1. Dabigatran dose (150 mg BID versus 110 mg BID) and 2. Time to initiation of therapy (0-2 days, 3-7 days and > 7 days). All results including baseline patient characteristics will be stratified by use of warfarin prior to the event and by the dabigatran dose after the event as described in **appendices 2-4**.

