### **7.2 Hypotheses Statements:**

Not applicable. The study is hypothesis generating only.

**7.3 Interim Analyses.** No interim analyses are planned.

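### Section 3.2 says the registry can determine whether dabigatran is within 0.5 to 2.5 intracranial hemorrhages per 100 patient-years, but 500 patients followed for 30 days cannot show this even with zero events

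*Combined protocol and SAP*

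**What the plan says.** Section 3.2 argues for a single-arm registry over a randomized comparison with warfarin. It says a safety threshold has been set from rates of warfarin-associated intracranial hemorrhage, "which have been reported to be 0.5 to 2.5 per 100 patient years", and concludes: "The registry design therefore permits determination of whether or not dabigatran is within this threshold". Section 3.1 adds: "Safety will be established by demonstrating low rates of hemorrhage in this setting". The first objective in 2.2 is: "Demonstrate the safety of early dabigatran initiation after minor stroke/TIA in patients with atrial fibrillation".

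The registry enrols 500 patients (7.1). On follow-up, 6.2.2 says: "The study outcome event period is 30 days from drug initiation". The primary outcome (5.1.2) is "PH2 associated with clinical deterioration, defined as worsening of NIHSS score of 4 or more points, within 30 days of initiating dabigatran therapy".

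On analysis, 7.1 says: "The primary and secondary outcomes will be defined with descriptive statistics". Rates are to be percentages of patients enrolled. No confidence interval, decision rule or conversion to person-time is mentioned. Section 7.2 says: "The study is hypothesis generating only". The synopsis entry on sample size says there are too few data on which to base one. Section 2.3 expects a symptomatic hemorrhagic transformation rate of 0.6%.

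**The concern.** The threshold is a rate per patient-year, and a 30-day study of 500 patients accrues very little person-time. At the rates in question about one event or none is expected, so a low count says little about whether the true rate is below 2.5.

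This matters because the sentence is the stated reason that a single arm can answer the safety question. Zero or one event gives a point estimate at or below 2.5, and with no interval planned it could be reported as within the threshold. There is also a unit hazard. The plan reports 30-day percentages while the threshold is annual, so the expected 0.6% looks comfortably inside 0.5 to 2.5 if the units are overlooked.

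The endpoints differ as well. The threshold concerns intracranial hemorrhage, while the primary outcome is the narrower PH2 with neurological worsening. The shortage of person-time applies to either endpoint.

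**Working it through.** **Inputs.** 500 patients (7.1); 30 days each (6.2.2); threshold 0.5 to 2.5 per 100 patient-years (3.2); expected rate 0.6% (2.3). The documents give no confidence level. I assume 95%, one- and two-sided, and then relax it. I read within leniently, as not above 2.5, and assume no loss to follow-up.

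**The plan's own figures.** The 500 cannot be reproduced, because no formula or target is given for it. The 0.6% can: 1.7% × 1/3 = 0.567%, which rounds to 0.6%.

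**Person-time.** T = 500 × 30/365.25 = 41.07 patient-years.

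**Expected events at the threshold.** 0.005 × 41.07 = 0.21; 0.025 × 41.07 = 1.03.

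**Exact Poisson limits for k events.** Two-sided 95%: lower χ²(0.025; 2k)/(2T), upper χ²(0.975; 2k+2)/(2T). For k = 0 the upper limit is −ln(α)/T: 2.996/41.07 = 7.29 per 100 patient-years (one-sided) and 3.689/41.07 = 8.98 (two-sided). Per 100 patient-years:

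| Events | Rate | Two-sided 95% interval | One-sided 95% lower | One-sided 95% upper |
|---|---|---|---|---|
| 0 | 0 | 0 to 8.98 | 0 | 7.29 |
| 1 | 2.43 | 0.06 to 13.57 | 0.12 | 11.55 |
| 2 | 4.87 | 0.59 to 17.59 | 0.87 | 15.33 |
| 3 | 7.30 | 1.51 to 21.35 | 1.99 | 18.88 |
| 4 | 9.74 | 2.65 to 24.94 | 3.33 | 22.29 |

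No row has an upper limit at or below 2.5. The best case exceeds it by a factor of 7.29/2.5 = 2.9 or 8.98/2.5 = 3.6. A lower limit first passes 2.5 at 4 events, under either convention.

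**Sensitivity.**
- Zero events at one-sided 90%: upper limit 5.61. At one-sided 80%: 3.92. Both exceed 2.5.
- If the true rate were exactly 2.5, zero events would occur with probability exp(−1.027) = 0.36. Zero events therefore supports a rate below 2.5 with only 64% confidence.
- Adding the 7 extra SAE days in 6.2.2 (37 days, 50.65 patient-years): zero-event upper limit 5.91 one-sided, 7.28 two-sided.
- Patients needed for zero events to give an upper limit of 2.5 over 30 days: 2.996/0.025 = 119.8 patient-years, or 1,459 patients (one-sided); 3.689/0.025 = 147.6 patient-years, or 1,797 patients (two-sided).

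**What is likely to be seen.** A rate of 2.5 per 100 patient-years is 2.5% × 30/365.25 = 0.205% over 30 days.
- Binomial(500, 0.00205): probability of 0 or 1 event 73%; of 4 or more, 2%.
- Binomial(500, 0.006): 20% and 35%.

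**The expected rate against the threshold.** Section 2.3 gives no time window for 0.6%. If it accrues over the 30-day outcome period at constant hazard (an assumption), it means 3 events, or 0.6 × 365.25/30 = 7.3 per 100 patient-years, 2.9 times the upper bound. It falls to 2.5 only if it accrues over 0.6 × 365.25/2.5 = 87.7 days. The expected point estimate is thus above the threshold on the 30-day reading, although the interval for 3 events (1.51 to 21.35) includes 2.5.

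**Inputs to the 0.6%.** Section 1.1 gives 1.7% as an increase in hemorrhagic transformation with early heparin. Section 2.3 gives it as the risk of symptomatic transformation on heparin. The one-third ratio in 2.3 is relative to warfarin but is applied to that heparin figure.

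**The case against.** The strongest defence is that the protocol does not rely on the threshold. It appears once, in the design rationale, and sets no sample size, stopping rule or analysis. Section 7.2 disclaims hypotheses, the Limitations text in section 7 calls the study small and a pilot, and the synopsis admits that the sample size has no data behind it. Section 3.2 also gives ethical and practical reasons for a single arm. All of this is true, and it limits the damage to the conclusion rather than to study conduct. It does not withdraw the sentence in 3.2, and the synopsis, 2.2 and 3.1 repeat the demonstrative aim.

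A second defence is that the documents set no confidence level, so the 95% standard is imported. That is fair as a condition on the wording, but zero events fails at one-sided 80% too.

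A third is that 3.2 claims only to determine whether or not dabigatran is within the threshold, and an excess is detectable. That stands. What fails is the favourable direction, which is the one the aim needs.

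Finally, the comparison of 0.6% with the threshold depends on an assumed window, and 2.3 does label its extrapolation a hypothesis. The main finding does not use the 0.6%.

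**Conclusion.** The concern holds, and the text should be corrected before the protocol is relied on. Section 3.2 states a property the design lacks: at conventional confidence, no possible result shows that dabigatran is at or below 2.5 per 100 patient-years, and the shortfall in the best case is a factor of 2.9 to 3.6. The registry can show only an excess. The result rests on 500 patients with complete 30-day follow-up and exact Poisson limits; loss to follow-up would make it worse. Confidence is high on this core point. The contrast between 0.6% and the threshold is secondary and depends on the 30-day, constant-hazard reading.

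**What to change.** - **3.2:** delete the sentence claiming determination. A weaker alternative is to restate the benchmark as a 30-day proportion for the same endpoint as the primary outcome and list the event counts that would exclude it. Simply converting 2.5 to 0.205% would not help, because 0/500 has an upper limit of 0.74% and only an excess could be shown.
- **7.1 and synopsis:** report the primary rate with an exact (Clopper-Pearson) two-sided 95% confidence interval, and state the precision that 500 patients give: 0/500, upper limit 0.74%; 3/500, 0.12% to 1.74%.
- **Synopsis, 2.2 and 3.1:** replace the aim of demonstrating or establishing safety with estimating the 30-day rate, in line with 7.2.
- **2.3:** state the time window for the 0.6%, reconcile the 1.7% with section 1.1 against the cited source, and say plainly that a ratio versus warfarin is being applied to a heparin figure.

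The cost is wording plus one interval, with no extra patients. The stated claim becomes less favourable, and the case for a single arm in 3.2 would rest on its practical and ethical arguments without the threshold.
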